BIOMEDICAL RESEARCH PROTOCOL
UNIVERSITY OF MISSOURI

Project Title: **A Prospective, Randomized, Non-Blinded, Crossover Controlled Clinical Trial Evaluating the Efficacy of Face Mask Ventilation with 45 Degree Head Rotation in Anesthetized Obese (BMI \geq 35) Adults**

IRB Number: 2012364

Version Number: 1

Version Date: 08/24/2018

Principal Investigator: [name]

Funding Source: Departmental

Clinicaltrials.gov Number: NCT03876873

PI: [name]^{1, 2}
Associate Professor

Co-I: [name], BS²
Medical Student

Co-I: [name], BS, BHS^{1, 2}
Research Specialist

¹Department of Anesthesiology and Perioperative Medicine

²School of Medicine

University of Missouri

Columbia, Missouri 65212

Primary Contact: [name]

Department of Anesthesiology and Perioperative Medicine

University of Missouri–Columbia

[name]

Columbia, MO 65212

[contact]

[contact]

Email: [contact]

2.1 Objectives:

This prospective, randomized, non-blinded, crossover controlled clinical trial will enroll subjects with a BMI ≥ 35 who are undergoing elective surgical procedures. Subjects will be randomized to receive mask ventilation after general induction of anesthesia in either a neutral head position (practice standard position) or a head rotation position (45 degree angle) to determine:

Primary Endpoint:

1. Maximal and average expiratory tidal volume during mask ventilation

Secondary Endpoints:

1. Maximal and average inspiratory tidal volume during mask ventilation
2. Maximal and average end-tidal CO₂ (ETCO₂) during mask ventilation
3. Maximal and average airway flow L/min during mask ventilation
4. Lowest and delta O₂ saturation drop on SpO₂ during mask ventilation
5. Lowest and delta O₂ saturation drop on SpO₂ during intubation

2.2 Clinical Hypotheses:

Primary Hypothesis:

We hypothesize that a 45 degree head rotation during mask ventilation will:

1. Increase the efficacy of mask ventilation measured by tidal volumes

Exploratory Hypotheses:

We hypothesize that a 45 degree head rotation during mask ventilation will:

1. Decrease upper airway obstruction measured by airway flow
2. Improve oxygenation measured by SpO₂ during mask ventilation
3. Improve oxygenation measured by SpO₂ during intubation

3.1 Background & Rationale:

Mask ventilation is a foundation of airway management after the initial induction of anesthesia. It allows for adequate oxygenation of the patient to buy enough time for intubation, during which the patient is not ventilated. However, in some patients mask ventilation may be difficult – older than 55 years, heavier (BMI > 26 kg/m²), with no teeth, having a beard or sleep apnea.^{1,2,3} Inadequate ventilation, if not corrected, can result in decreasing oxygen saturation to dangerous levels – which could lead to devastating complications. As a result, the efficacy of mask ventilation is of critical importance to patient safety after the induction of anesthesia.

[figure not shown]
A recent study proposed that mask ventilation could be improved simply by turning a patient's head. The study showed that rotating a patient's head to a 45 degree angle significantly improved mask ventilation when compared with the head placed in a neutral position.⁴ However, this study was done in patients with a BMI less than 35. As such, the effects of head rotation on the efficacy of mask ventilation has not been studied in patients with a BMI of 35 and greater.

Obesity (BMI \geq 30 kg/m²) affects almost 40% of US adults and is one of the most prevalent health concerns in our society.⁵ It is a predictor of difficult mask ventilation because it is associated with increased upper airway obstruction, decreased airway patency, and decreased lung volumes such as functional residual capacity (FRC).¹ If previous findings in regard to the effect of 45 degree head rotation on the efficacy of ventilation hold true in the obese patient, then this study will show that head rotation could be used as a simple way to improve the efficacy of mask ventilation for patients with a BMI of 35 and above.⁴

4.1 Study Design:

This will be a prospective, randomized, crossover, non-blinded, controlled clinical trial performed at a single academic hospital.

4.2 Study Design:

4.3 Study Procedures:

I. Subject Population: this study will enroll 38 adults undergoing elective surgery requiring general anesthesia with intubation of the trachea.

II. Inclusion Criteria:

- a. Age \geq 18 years
- b. ASA I-III
- c. BMI \geq 35 kg/m²

III. Exclusion Criteria:

- a. Inability to obtain written informed consent
- b. Pregnant or breastfeeding
- c. Limited head rotation or neck extension
- d. Subjects with expected or history difficult intubation
- e. Large beard
- f. OG/NG tube
- g. GERD

IV. Randomization: On the day of surgery, before the induction of anesthesia subjects will be randomized into either Group A or Group B. Randomization will be accomplished by the method of randomized permuted block. The two groups will be stratified so that obese subjects with a BMI ≥ 35 and ≤ 44 and those with a BMI ≥ 45 are equally distributed between both groups. Groups will be additionally stratified by the presence or lack of obstructive sleep apnea (OSA).

V. Blinding: Group assignment will not be known by research staff at the time of subject recruitment. No blinding will occur during the clinical portion of the study or during data analysis.

VI. Preoperative Data Collection and Measurements: Before the subject is taken into the operating room, we will record and measure age, BMI, sex, ASA status, preop diagnoses, OSA, procedure being done, Mallampati score, mouth opening, thyromental distance, neck circumference, neck range of motion, lack of teeth, presence of beard, and history of snoring.

VII. Anesthetic Management

a. Monitoring

1. All subjects will be monitored with standard perioperative monitors: ECG, non-invasive blood pressure, pulse oximetry, esophageal temperature, and capnography.

b. Anesthetic Technique

1. All subjects will receive a standardized general anesthetic technique and all anesthetic medications will be dosed on the ideal body weight rather than actual body weight.
2. Preoxygenation – 100% oxygen delivered via face mask for a minimum of 3 minutes

3. Induction – intravenous delivery of propofol, 1.5-2.0 mg/kg, fentanyl, 1 µg/kg, and rocuronium, 0.6 mg/kg. Additional propofol or fentanyl may be administered at the discretion of the anesthesia provider.
4. Mask Ventilation – start when subject loses consciousness. Ventilation settings will be pressure controlled ventilation 20 cmH₂O. Respiratory Rate will be 16. Group A will receive 1 minute of neutral head position followed by 1 minute of 45 degree head rotation to the right and then 1 minute of neutral head position. Group B will be the opposite. If mask ventilation is difficult or SpO₂ saturation drops below 90% the subject will be excluded from the study. Immediately after exclusion the standard of care ventilation will be resumed.
5. Intubation – will be in the standard of care fashion after the 3 sets of head positions are completed. Usually the endotracheal intubation is after 2-3 minutes after induction. Our study may increase that time by 1 or 2 minutes.
6. The study will conclude with intubation of the trachea. The rest of the subject management will be per anesthesia clinical team standard of care.

c. Extubation

1. Standard of care.

VIII. Postoperative Pain Management

a. Standard of care.

4.4 Costs:

The cost of the Medline Top Valve Anesthesia Mask used in this study will be billed to subjects' insurance as normal standard of care at University Hospital. Face masks are used on surgical patients as standard of care following University Hospital Department of Anesthesiology and Perioperative Medicine protocol. They are necessary for

preoxygenation of patients before surgical procedures. Taking part in this study will bring no additional cost to subjects.

4.5 Study Duration:

Study will start in September 2018 and last one year.

5.1 Statistical Analysis and Sample Size Justification:

A power analysis using a predicted tidal volume of 450 ml for group A and 520 ml for group B, with a standard deviation of 75 ml, determined that 19 subjects per group would be needed to achieve a power of 80% with an alpha error of 5%.

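### Maximal expiratory tidal volume shares unranked primary status with the average, although the best of about 16 breaths can fail to register lost ventilation

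*Combined protocol and SAP*

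**What the plan says.** Section 2.1 gives one primary endpoint made of two summaries: "Maximal and average expiratory tidal volume during mask ventilation". It does not say which decides the trial, or what follows if they disagree. The primary hypothesis in 2.2 is that rotation will "Increase the efficacy of mask ventilation measured by tidal volumes", again without naming a summary.

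Section 4.3, VII.b.4 fixes the breaths that feed these summaries. The mode is "pressure controlled ventilation 20" (in cmH₂O), and the rate is set by the words "Respiratory Rate will be 16". On timing, the first two minutes of one sequence are given as "Group A will receive 1 minute of neutral head position followed by 1 minute of 45 degree head rotation to the right". A third minute returns that sequence to neutral, and the other sequence runs rotated, neutral, rotated.

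Section 5.1 starts: "A power analysis using a predicted tidal volume of 450 ml for group A and 520 ml for group B". It adds an SD of 75 ml and arrives at 19 subjects per group. It does not say whether these volumes are averages or maxima. It gives no analysis method, no rule for extracting the maximum or handling artefact breaths, and no breath-level variability.

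**The concern.** The hypothesis concerns how well the patient is ventilated. An average over the minute answers that, because every breath counts. A maximum keeps one breath and discards the other 15 or so.

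Two consequences follow. First, the expected maximum is the mean plus a multiple of the breath-to-breath SD, so a difference in maxima mixes a difference in ventilation with any difference in steadiness. Second, under pressure control, loss of patency appears as small breaths. If some breaths in a minute are lost and others are clear, the average falls but the best breath hardly changes.

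At stake is the meaning of the primary result. With two unranked summaries, a benefit seen clearly on the average could sit beside a null result on the maximum, and the plan gives no basis for saying which one is the trial's answer.

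**Working it through.** **The plan's own figure.** Inputs from 5.1: difference 520 − 450 = 70 ml, SD 75 ml, power 80%, alpha 5% (taken as two-sided).

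n per group = 2 × (1.960 + 0.842)² × 75² / 70² = 18.02, rounded up to 19. This reproduces the stated figure. A two-sample t calculation gives 19.03, with power 79.9% at 19 per group. The figure is a parallel-group one, and the point made here does not change it.

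**Breaths per maximum.** From 4.3, VII.b.4: 16 per minute × 1 minute = about 16.

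**What a maximum estimates.** For m independent normal breaths, expected maximum = mean + c(m) × breath SD, with c(16) = 1.765. The difference between positions is therefore

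- in averages: difference in means;
- in maxima: difference in means + 1.765 × (difference in breath SDs).

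**Case 1: uniform obstruction, equal breath SDs.** Means 450 and 520 ml, assumed breath SD 40 ml in both positions (1.765 × 40 = 71). Expected maxima are 450 + 71 = 521 and 520 + 71 = 591 ml. The difference is 70 ml, the same as for the averages, so the two summaries agree.

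**Case 2: some breaths lost, common level for clear breaths.** Assumed: clear breaths average 480 ml in both positions, breath SD 40 ml, and 30% of neutral breaths cut to 250 ml.

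- Neutral average = 0.7 × 480 + 0.3 × 250 = 336 + 75 = 411 ml. Rotated average = 480 ml. Difference = 69 ml.
- In neutral, the maximum is in practice the best of the clear breaths, on average 0.7 × 16 = 11.2 of them. Averaged over the binomial number of clear breaths, the multiplier is about 1.587 instead of 1.765. Difference in maxima = (1.765 − 1.587) × 40 = about 7 ml.

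So the maximum records about a tenth of the loss (7/69).

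**How often each would be significant in case 2.** Simulation of 4,000 trials per setting: 38 subjects, 19 per sequence, neutral-rotated-neutral and rotated-neutral-rotated, one average and one maximum per minute. The contrast is rotated minus neutral within subject, using the mean of same-position minutes, averaged over the two sequences, with a t test on 36 df. The 75 ml SD is assumed to apply at minute level, with within-subject correlation 0.5, 0.8 or 0.9.

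- Average: about +69 ml, significant in at least 99.9% of trials.
- Maximum: about +7 ml, significant for rotation in roughly 9% (correlation 0.5) to 20% (correlation 0.9).

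**Unequal breath SDs.** With equal means and assumed breath SDs of 60 and 40 ml, the maxima differ by 1.765 × 20 = 35 ml with no difference in average ventilation. The multiplier assumes independent breaths. With serial correlation of 0.5, 0.8 and 0.9 between successive breaths it falls to 1.62, 1.29 and 1.01, and the 35 ml falls to 32, 26 and 20 ml.

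All of this takes one maximum per minute, so it does not arise from one position being held for two minutes and the other for one.

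**The case against.** The strongest reply is that the average is already in the primary endpoint. In case 2 it detects the benefit almost every time, so the plan as a whole does not miss it; only one of its two statistics does. That stands, and it limits the point to the equal, unranked standing of the maximum.

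Second, section 3.1 speaks of more upper airway obstruction and less patency in obesity but never says the obstruction is intermittent. If it is sustained and partial, case 1 applies and nothing is lost. This also stands: case 2 shows what can happen and is not a forecast. Section 4.3 also removes subjects in whom mask ventilation proves difficult, a term it does not define, so some of those with many lost breaths might not be analysed.

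Third, a reader might infer that the maximum would make the worse position look better. The documents do not support that as an expectation. Under pressure control, obstruction takes volume away; it does not create larger breaths. With a common level for clear breaths, case 2 still points towards rotation, only weakly. A reversal needs either clear breaths that are larger in the neutral position than in the rotated one, or larger breath-to-breath SDs in the worse position. At the planned means, the SD excess would have to be more than 70 / 1.765 = about 40 ml.

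A reader might also infer that variability alone would win the trial for rotation. That needs rotation to raise variability without changing the mean, for which the documents give no reason. It also needs a rule that the maximum alone can carry the primary claim, and the plan states none.

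**Conclusion.** The point holds as a low-cost improvement to a stated endpoint. The maximum is a function of both mean and variability, taken from one breath in about 16, and it can fail to register lost breaths. In the illustration it shows about 7 ml where the average shows about 69 ml. That contrast rests on assumed values (breath SD 40 ml, clear breaths at 480 ml, 30% of neutral breaths at 250 ml, independent breaths), and the 9-20% also on 75 ml as a minute-level SD and correlations of 0.5 to 0.9. With uniform obstruction and equal breath SDs there is no discrepancy. Neither a reversed result nor a false positive from variability alone should be claimed as expected. The firm part needs no assumed values: the plan gives both summaries equal primary standing, has no rule if they differ, and only the average uses every breath to measure the ventilation named in the hypothesis.

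**What to change.** In 2.1, make the average expiratory tidal volume over the breaths of each one-minute position the sole primary endpoint, and name that summary in the primary hypothesis in 2.2. In 5.1, state that the 450 and 520 ml values and the 75 ml SD refer to that average. If they do, 19 per group is unaffected by this edit; if 75 ml describes something else, the figure needs restating. Move maximal expiratory tidal volume to a descriptive or secondary measure, and say that it supports no efficacy claim by itself. A lower-tail summary of the same breaths is optional. It would show lost breaths directly, but it is itself open to artefact from head turning or re-seating the mask.

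The cost is one primary statistic. No new data, subjects or procedures are needed.

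### Does the gap between BMI 44 and BMI 45 in the randomisation strata need a change to the plan?

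*Combined protocol and SAP*

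**What the plan says.** Section 4.3 II sets the BMI entry criterion at 35 kg/m² or more and gives no upper limit. Section 4.3 IV describes the allocation: "Randomization will be accomplished by the method of randomized permuted block", with the aim that "obese subjects with a BMI ≥ 35 and ≤ 44 and those with a BMI ≥ 45 are equally distributed between both groups". Obstructive sleep apnea, present or absent, is a second stratification factor, so there are four cells. The section does not give the block size or the holder of the list.

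Section 4.3 V states that "Group assignment will not be known by research staff at the time of subject recruitment" and also that "No blinding will occur during the clinical portion of the study or during data analysis". Section 4.3 VI lists the preoperative data: "we will record and measure age, BMI, sex, ASA status" and further items. It does not give the precision to which BMI is recorded.

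Under section 4.3 VII.b.4, Group A has one minute neutral, one minute rotated and one minute neutral; Group B has the opposite. On size, "this study will enroll 38 adults undergoing elective surgery". Section 5.1 contains only the power calculation.

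**The concern.** BMI is a continuous quantity, and the two strata as written leave out every value strictly between 44 and 45. Such a subject is eligible but has no stratum, and no rule says what to do. Randomisation takes place on the day of surgery, so an unresolved case would have to be settled then or when the list is set up.

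The worry is discretion. Past assignments are visible because the trial is open, and the four cells are small. If the next assignment in a cell could be inferred from an almost complete block, then freedom to choose the cell would be some freedom to choose the group. The BMI stratum would also be undefined for that subject in any analysis that used it.

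**Working it through.** **1. The plan's own figure.** Section 5.1 uses a "predicted tidal volume of 450 ml for group A and 520 ml for group B, with a standard deviation of 75 ml", with 80% power and 5% alpha. For a two-sided comparison of two independent means,

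n per group = 2 × (1.960 + 0.842)² × 75² / 70² = 2 × 7.849 × 1.148 = 18.02, rounded up to 19.

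This reproduces the stated 19 per group. (The t-test version gives 19.03, with 79.9% power at 19.) BMI and the strata do not enter the calculation, so the gap cannot affect the sample size.

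**2. Which values are left out.** Check each eligible BMI against the two conditions in section 4.3 IV.

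- To one decimal: 44.1 to 44.9, nine values, meet neither.
- As a whole number, rounded or truncated: none is left out.
- The two conventions agree for 44.1 to 44.4 (lower stratum). For 44.5 to 44.9, truncation gives the lower stratum and rounding half up gives the upper. Either way the subject has a stratum.

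**3. How many subjects.** The documents give no BMI distribution, so this step rests on assumptions. With an exponential excess above 35 of mean m,

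P(44 < BMI < 45) = exp(−9/m) − exp(−10/m).

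| Assumption (decimal BMI) | Share in gap | Expected of 38 | Chance of at least one, 1 − (1 − p)³⁸ |
|---|---|---|---|
| m = 4 | 0.1054 − 0.0821 = 2.3% | 0.89 | 59% |
| m = 8 | 0.3247 − 0.2865 = 3.8% | 1.45 | 77% |
| p set at 2% | 2% | 0.76 | 54% |
| p set at 10% | 10% | 3.8 | 98% |

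With whole-number BMI, all these entries are zero.

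**4. What a placement can change.** Whichever cell the subject joins, the sequence comes from the next place in a randomly permuted block, so the assignment is still random. The direct consequence is that one subject may receive the other order. As a stress test, suppose this moves the sequence sizes from 19 and 19 to 18 and 20. For the treatment contrast averaged over the two sequences, the variance is proportional to 1/n₁ + 1/n₂:

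- 19 and 19: 2/19 = 0.10526
- 18 and 20: 1/18 + 1/20 = 0.10556, a ratio of 1.003

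An extreme version takes the 10% row, rounds 3.8 up to four subjects and moves all of them the same way, to 15 and 23. Then 1/15 + 1/23 = 0.11014, a ratio of 1.046. The standard error rises by a factor of √1.046 = 1.023, or about 2%.

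**5. Whether any planned analysis uses the stratum.** Section 5.1 names no subgroup, stratified or covariate-adjusted analysis. BMI itself is recorded under section 4.3 VI, so a later analysis could use the actual value.

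**The case for a change.** The strongest case for acting is that the defect is visible on the page, is likely to be met at least once if BMI has decimals, and could be cured by a small edit to one sentence and to the list. Whole-number BMI is an inference from the cut-points and is not stated. Rounding and truncation also disagree for half of the gap, so two careful people could stratify the same subject differently. Rounding sits awkwardly with the entry criterion as well, since 34.6 would become 35. With open assignments, 38/4 = 9.5 subjects per cell on average and no stated block size or concealment method, prediction of the next assignment cannot be ruled out.

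The wording point stands in full. The consequences do not carry the same weight:

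- Nothing in the protocol describes placement by hand; a list or program with a fixed convention would serve.
- Steering needs a subject in the gap, a predictable next assignment, different next assignments in the two candidate cells, and a motive. None of these is shown. Section 4.3 V says that staff do not know the assignment at recruitment. That does not prove concealment at the moment of randomisation, but it points away from foreseeable allocation.
- If blocks were predictable, the problem would concern all 38 subjects and would be a matter of concealment. Closing a gap one BMI unit wide would not cure it.
- A convention for choosing the stratum need not alter how eligibility is judged, so the 34.6 example does not arise.

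**Conclusion.** No change to the plan is called for. Read literally, the strata omit BMI values between 44 and 45, and the protocol gives no rounding rule. This is a small gap in wording that staff would fill sensibly, since a subject with a BMI of 44.5 sits on the boundary and fits either stratum.

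The size is about one subject in 38 under the exponential assumption with decimal BMI, up to 3.8 if as many as 10% fall in the gap, and none with whole-number BMI. The possible effect is on the order of head positions for those subjects. It does not decide which positions they receive. The cost in variance is about 0.3% for one subject moved and under 5% in the extreme case.

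This rests on two readings of the plan: that the comparison of head positions is made within subjects, as the crossover design implies, and that each placement takes the next assignment from the permuted list. Contiguous bounds would read more cleanly, but the estimate, the sample size and the conclusion would not gain from them.

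### Section 4.3 V rules out blinding of the data analysis, although the analyst could be masked to head position at small cost while breath, summary and model choices are still open

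*Combined protocol and SAP*

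**What the plan says.** Section 4.3 V conceals assignment only up to enrolment: "Group assignment will not be known by research staff at the time of subject recruitment". It then states: "No blinding will occur during the clinical portion of the study or during data analysis". No other section provides for a masked analyst, a masked reader or a coded data set.

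The primary endpoint in section 2.1 names two summaries without ranking them: "Maximal and average expiratory tidal volume during mask ventilation". The primary hypothesis in section 2.2 is directional, in that rotation is expected to increase tidal volume.

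Under Mask Ventilation in section 4.3 VII, the breathing frequency is fixed: "Respiratory Rate will be 16". The order of positions for the first arm is set out as follows: "Group A will receive 1 minute of neutral head position followed by 1 minute of 45 degree head rotation to the right". A second neutral minute closes that sequence. For the other arm the text says only: "Group B will be the opposite". Each subject therefore has three minutes, two in one position and one in the other.

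Section 5.1 holds only the sample size calculation and names no test or model.

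**The concern.** An open-label clinical phase is unavoidable here because whoever holds the mask sees the head. Leaving the analysis unblinded is a separate choice, and the plan gives no reason for it.

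The choice matters because so much is left to be settled after the data are in:

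- which breaths in each minute count, and what happens to leak or transition breaths;
- which of the two summaries is primary;
- how the repeated position is reduced to one value;
- which model is fitted.

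Someone making these decisions with the positions visible, and with a stated expectation that rotation is better, could move the contrast in that direction without intending to. Numerical outcomes protect each reading, but not the choice of readings. The maximal tidal volume is the most exposed, because it rests on a single breath.

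**Working it through.** **The plan's own figure.** Section 5.1 gives 450 and 520 ml, SD 75 ml, 80% power and 5% alpha. The difference is 520 − 450 = 70 ml. For two independent groups, two-sided, n = 2 × (1.960 + 0.842)² × (75/70)² ≈ 18.02, which rounds up to the stated 19 per group (38 in total). Power at 19 is 0.820 by the normal approximation and 0.799 by the t-test. Masking the analysis leaves this figure unchanged.

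**Breaths available.** A rate of 16 for one minute gives about 16 breaths per period and 3 × 16 = 48 per subject. If all minutes are used, one position has 16 breaths and the other 32. The two groups differ only in which position has 32.

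**Shift from selective deletion (average tidal volume).** Assume normally distributed breaths. The expected maximum, in SD units, is 1.766 for 16 breaths and 2.070 for 32. Dropping the most extreme of n breaths moves the mean of the rest by that value divided by (n − 1). One deletion in each position, in opposite directions, gives:

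1.766/15 + 2.070/31 = 0.118 + 0.067 = 0.185 breath-to-breath SD.

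The documents give no breath-to-breath SD. The 75 ml in section 5.1 is a planning SD for a two-group comparison and is not stated to be variation within one patient. A range is therefore shown:

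| Assumed SD (ml) | Shift (ml) | Share of 70 ml |
|---|---|---|
| 10 | 1.8 | 3% |
| 30 | 5.5 | 8% |
| 50 | 9.2 | 13% |
| 75 | 13.8 | 20% |

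These values need the deletion in every subject. If it happened in a quarter of subjects, the shift would be a quarter as large (13.8/4 ≈ 3.5 ml at the top of the range).

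**What a consistent shift does to the error rate.** Assume no true effect, a paired t-test on 38 subjects, SD 75 ml in each position and within-subject correlation ρ. None of these analysis assumptions is stated in the plan. The SD of the difference is 75 × √(2(1 − ρ)), which is 106, 75 and 47 ml at ρ = 0, 0.5 and 0.8. The two-sided 5% error then becomes:

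| Shift | ρ = 0 | ρ = 0.5 | ρ = 0.8 |
|---|---|---|---|
| 5 ml | 5.9% | 6.9% | 9.7% |
| 10 ml | 8.7% | 12.6% | 24.4% |

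**What masking does not reach.** Picking whichever of the maximal and average results is significant gives an error of 1 − 0.95² = 9.75% if the two tests are independent. It is about 9.1% to 7.0% if the test statistics correlate at 0.5 to 0.9. This applies whether or not the positions are coded.

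**Whether coding can work.** Group A is neutral-rotated-neutral and Group B, read as its opposite, is rotated-neutral-rotated. Coded, the patterns are P-Q-P and Q-P-Q, and neither reveals which letter is rotation. The Group A/B label does reveal it, so it must be withheld too.

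**The case against.** The strongest reply is that the mechanism is assumed. No section describes excluding a breath, and the plain reading of the endpoint is every breath in the minute. The outcomes are numerical and ventilation is at fixed pressure and rate, so breath-to-breath variation may be small and the room for bias narrow. The trial also declares itself non-blinded throughout. All of this stands, and it is why the point is an open possibility of uncertain and perhaps small size.

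A second reply is that coding does less than it appears to:

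- It does not stop an analyst choosing the summary with the larger P-Q gap.
- Period boundaries depend on when the head was turned, which only unblinded bedside staff can note.
- An effect near 70 ml would suggest which letter is rotation once the means are seen.
- Mask handling stays unblinded, as does the judgement in "If mask ventilation is difficult or SpO₂ saturation drops below 90% the subject will be excluded from the study".

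This also stands. A reader might infer that masking the labels closes the path to bias. It does not. It reduces directional bias in data handling and has to accompany prespecification.

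A reader might also count 16 breaths in each position and obtain 2 × 1.766/15 = 0.235 SD, or 12-18 ml (17-25% of 70 ml) at SD 50-75 ml. That needs one deletion in each of the three minutes, or one minute set aside. The documents provide for neither. It also shows only the upper end of the assumed SDs.

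Finally, the documents do not say who analyses the data or who attends cases, so the low cost is a judgement. For 38 subjects it is a reasonable one.

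**Conclusion.** The point holds as a minor, inexpensive improvement. The plan expressly declines masked analysis, nothing elsewhere offsets this, and the derivation and analysis rules that would otherwise limit discretion are absent.

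Under the illustration the shift in the contrast is 0.185 breath-to-breath SD: about 2-6 ml at SD 10-30 ml and 9-14 ml at SD 50-75 ml, or 3-20% of the planned difference. It is proportionally less if only some subjects are affected. The result rests on normally distributed breaths, one opposed deletion per position, use of all three minutes, and SDs that the documents do not supply.

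A reader might infer that selective handling of breaths is planned, or that the sample size is affected. The documents support neither: they describe no exclusion step, and 19 per group reproduces and stays as it is.

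**What to change.** Revise section 4.3 V to state that:

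1. clinical care is unblinded, and the start and end time of each period is recorded at the bedside;
2. before any derivation, an existing team member who does not analyse the data recodes head positions as P/Q and withholds the Group A/B label;
3. breath exclusions, endpoint derivation and the primary model are completed, in that order, and locked on the coded data before the code is broken.

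Alongside this, state in sections 2.1 and 5.1, before any data are examined, the rule for which breaths count, the single primary summary, how the repeated minutes are combined, and the model. Bias from unblinded mask handling and from the bedside exclusion for difficult ventilation is not addressed by these changes and should be acknowledged as a limitation.

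The cost is a short text change and a small recoding and locking step for 38 subjects. No patient procedure changes and no subjects are added.
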